8.2 Study Setting and Data Sources

Integrated Primary Care Information Project (IPCI), The Netherlands (Erasmus)

IPCI is collected from electronic health records (EHR) of patients registered with their general practitioners (GPs) throughout the Netherlands. The selection of 374 GP practices is representative of the entire country. The database contains records from 2.8 million patients out of a Dutch population of 17M starting in 1996. The median follow-up is 2.6 years. The observation period for a patient is determined by the date of registration at the GP and the date of exit/death. The observation period start date is refined by many quality indicators, e.g. exclusion of peaks of conditions when registering at the GP. All data before the observation period is kept as history data.³

Information System for Research in Primary Care (SIDIAP), Spain (IDIAP Jordi Gol)

SIDIAP is collected from EHR records of patients receiving primary care delivered through Primary Care Teams (PCT), consisting of GPs, nurses and non-clinical staff. The Catalan Health Institute manages 286 out of 370 such PCT with a coverage of 5.6M patients, out of 7.8M people in the Catalan population (74%). The database started to collect data in 2006. The mean follow-up is 10 years. The observation period for a patient can be the start of the database (2006), or when a person is assigned to a Catalan Health Institute primary care centre. Date of exit can be when a person is transferred-out to a primary care centre that does not pertain to the Catalan Health Institute, or date of death, or date of end of follow-up in the database.⁴

Clinical Practice Research Datalink GOLD, United Kingdom (University of Oxford)

The Clinical Practice Research Datalink (CPRD) is a governmental, not-for-profit research service, jointly funded by the National Institute for Health and Care Research and the Medicines and Healthcare products Regulatory Agency, a part of the Department of Health, United Kingdom (UK) (<https://cprd.com>). CPRD GOLD comprises computerized records of all clinical and referral events in primary care in addition to comprehensive demographic information and medication prescription data in a sample of UK patients (predominantly from Scotland (52% of practices) and Wales (28% of practices). Data are available for 20 million patients, including 3.2 million currently registered patients.⁵

IQVIA Longitudinal Patient Database (LPD) Belgium

IQVIA LPD Belgium is a computerised network of GPs who contribute to a centralised database of anonymised data of patients with ambulatory visits. Currently, around 300 GPs from 234 practices are contributing to the database covering 1.1M patients from a total of 11.5M Belgians (10.0%). The database covers time from 2005 through the present. Observation time is defined by the first and last consultation dates.

	D2.2.3 – Study Protocol for C1-001	
	Author(s): [name], [name], [name], [name]	Version: 2.0 - Final
	Dissemination level: Public	

IQVIA Disease Analyser (DA) Germany

IQVIA Disease Analyser (DA) Germany is collected from extracts of patient management software used by GPs and specialists practicing in ambulatory care settings. Data coverage includes more than 34M distinct person records out of a total population of 80M (42.5%) in the country and collected from 2,734 providers. Patient visiting more than one provider are not cross identified for data protection reasons and therefore recorded as separate in the system. Dates of service include from 1992 through present. Observation time is defined by the first and last consultation dates. Germany has no mandatory GP system and patients have free choice of specialist. As a result, data are collected from visits to 28.8% General, 13.4% Orthopaedic Surgery, 11.8% Otolaryngology, 11.2% Dermatology, 7.7% Obstetrics/Gynaecology, 6.2% various Neurology and Psychiatry 7.0% Paediatric, 4.6% Urology, 3.7% Cardiology, 3.5% Gastroenterology, 1.5% Pulmonary and 0.7% Rheumatology practices.

Table 2. Description of the selected Data Sources.

Country	Name of Database	Justification for Inclusion	Health Care setting (e.g. primary care, specialist care, hospital care)	Type of Data (EHR, claims, registries)	Number of active subjects
The Netherlands	Integrated Primary Care Information Project (IPCI)	Database selected for Y1 of Darwin EU® and has information on blood cancers	Primary care	EHR	1.4 million
Spain	Sistema d'Informació per al Desenvolupament de la Investigació en Atenció Primària (SIDIAP)	Database selected for Y1 of Darwin EU® and has information on blood cancers	Primary care with hospital linkage	EHR	5.8 million
United Kingdom	The Clinical Practice Research Datalink (CPRD) GOLD database	Database selected for Y1 of Darwin EU® and has information on blood cancers	Primary care	EHR	3 million
Belgium	IQVIA Belgium	Database selected for Y1 of Darwin EU® and has information on blood cancers	Ambulatory EMR (GP + SP)	EHR	435,200

	D2.2.3 – Study Protocol for C1-001	
	Author(s): [name], [name], [name], [name]	Version: 2.0 - Final
	Dissemination level: Public	

Country	Name of Database	Justification for Inclusion	Health Care setting (e.g. primary care, specialist care, hospital care)	Type of Data (EHR, claims, registries)	Number of active subjects
Germany	IQVIA DA Germany	Database selected for Y1 of Darwin EU® and has information on blood cancers	Ambulatory EMR (GP + SP)	EHR	8.5 million

ALL: acute lymphocytic leukaemia, AML: acute myeloid leukaemia, CLL: chronic lymphocytic leukaemia, MM: multiple mieloma, DLBCL: diffuse Large B-Cell Lymphoma, FNHL: follicular lymphoma

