6. RATIONALE AND BACKGROUND

The Committee for Orphan Medicinal Products (COMP) is the European Medicines Agency's (EMA) committee responsible for recommending orphan designation of medicines for rare diseases. It was established in 2000 when new legislation was introduced to encourage the development of medicinal products for rare diseases. One important criterion for granting an orphan designation to a medicine is a prevalence threshold of maximum 5 in 10,000 for the associated condition at the time of application. Of the submissions to the COMP, around 35% are for oncological conditions and around 42% of designations of orphan medicinal products in oncology granted by the COMP between 2000 and 2015 related to rare haematological malignancies.¹

Prevalence estimates, such as of rare haematological malignancies, are a frequent source of uncertainty when submissions to the COMP are being assessed.² In particular, limited availability of population-based epidemiological studies has often led to the use of indirect methods for calculations of prevalence which often involves various assumptions. In addition, time trends in prevalence may also be present meaning that certain conditions that previously satisfied the prevalence criterion for orphan designation in the past may no longer do so. Indeed, increased prevalence has previously been noted for a number of rare haematological malignancies, which may be explained by improved survival and aging populations.¹ In this study the prevalence of rare blood cancers will be measured in Europe over time.

	D2.2.3 – Study Protocol for C1-001	
	Author(s): [name], [name], [name], [name]	Version: 2.0 - Final
	Dissemination level: Public	

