8.3 Study Period

The study period will be between 1st January 2010 and the end of available data in each of the data sources.

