8.6.2. Outcome/s (where relevant)

Outcome cohort definitions for partial and complete prevalence

Complete prevalence represents the number of persons alive at the specific point in time regardless of how long ago the diagnosis was, while partial prevalence limits the number of patients to those diagnosed during a fixed time in the past.⁶ To operationalise this definition outcome cohorts will be defined which vary in how the cohort exit is defined. For complete prevalence an individual will remain in the outcome cohort until the end of their observed time at risk. Meanwhile, for partial prevalence, an individual will exit the outcome cohort after a certain number of days has elapsed since the first record indicating them to be a prevalent case (e.g. 1,825 days for 5-year partial prevalence).

Follicular lymphoma

Follicular lymphomas are the second leading Non-Hodgkin’s lymphomas and can be diagnosed accurately on morphologic findings alone: B-cell in follicular centre. Many patients are diagnosed incidentally or at a time when their lymphoma is not causing symptoms or signs of organ function impairment. The major differential diagnosis is between lymphoma and reactive follicular hyperplasia. The coexistence of diffuse large B-cell lymphoma must be considered. Patients with follicular lymphomas are often subclassified, or graded, into those with predominantly small cells, those with a mixture of small and large cells, and those with predominantly large cells. The typical natural history is a pattern of continuous relapses with a diminishing sensitivity to chemotherapy. On average, most patients will live with follicular lymphoma for 15 to 20 years.

For this study, cases will be identified based on a record indicating a diagnosis or observation of follicular lymphoma. A clinical description along with a preliminary code list is provided in Appendix 1. For the primary analysis, 5-year partial prevalence will be estimated and so individuals will be considered as a prevalent case if they had a relevant record observed in the prior 1,825 days. In sensitivity analyses, 2-year partial prevalence

	D2.2.3 – Study Protocol for C1-001	
	Author(s): [name], [name], [name], [name]	Version: 2.0 - Final
		Dissemination level: Public

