8.8 Analysis

Prevalence summarises the total number of individuals who have the outcome of interest at a particular time or during a particular period divided by the population at risk of having the outcome at that time or during the period. Point prevalence gives the proportion of individuals in a population who have the outcome at a given point in time, while period prevalence gives the proportion of individuals with the outcome at any time during a specified time period or interval. A key aspect here is that an outcome is defined in the sense of having a duration, with a start and an end date. As mentioned above, in partial prevalence the outcome end date is determined by a fixed number of days since the first record of the outcome event whereas in complete prevalence the outcome end date is defined as the end of observation time for an individual who has at some point prior had a record of the outcome.

For an example of calculations of point and period prevalence under partial prevalence see **Figure 3** below. It can be seen that at time $t+2$, two of the five study participants are in an outcome cohort giving a point prevalence of 40%. Period prevalence between $t+2$ and $t+3$ in this simple example would give the same answer. However, for the period t to $t+1$ the result will depend on whether study participants are required to have been observed for the full study period. If no such restriction is imposed all five study participants would contribute, but if study participants had to have been observable for the full period, then only three of the study participants would contribute.

In this study the primary analysis will use point prevalence, estimated as of the 1st January of each calendar year. We will also estimate period prevalence as a sensitivity analysis, estimated on an annual basis (between the 1st January and 31st December for each year). Period prevalence will first be estimated with participants required to contribute a minimum of only one day of the period to be included. Subsequently, we will estimate period prevalence with participants required to be observed for the full period for them to be included.

	D2.2.3 – Study Protocol for C1-001	
	Author(s): [name], [name], [name], [name]	Version: 2.0 - Final
	Dissemination level: Public	

[figure not shown]

Figure 3. Point and period prevalence

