23	Sensitivity	Period prevalence (annual)	0 days	Full year
24	Sensitivity	Point prevalence	1095 days	N/A
25	Sensitivity	Period prevalence (annual)	1095 days	One day
26	Sensitivity	Period prevalence (annual)	1095 days	Full year

*For 5-year partial prevalence individuals will be considered as a prevalent case if they had their initial diagnosis observed in the prior 1,825 days. *For 2-year partial prevalence will be considered as a prevalent case if they had a relevant record observed in the prior 730 days. †For complete prevalence individuals will be considered as a prevalent case if they have ever had a relevant record previously.

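### SIDIAP data start in 2006, too late to fill the 5-year window on 1 January 2010, and its complete-prevalence trend partly reflects a lengthening look-back

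*Protocol*

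**What the plan says.** Section 8.3 sets one calendar start for all five sources: "The study period will be between 1st January 2010 and the end of available data in each of the data sources". Section 8.8 fixes the index dates: "In this study the primary analysis will use point prevalence, estimated as of the 1st January of each calendar year". The primary measure counts a person as prevalent if the diagnosis falls within a fixed window, given in section 8.6.2 as "1,825 days for 5-year partial prevalence".

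Section 8.2 gives different data starts. For SIDIAP, "The database started to collect data in 2006". For IQVIA Belgium, "The database covers time from 2005 through the present". IPCI goes back to 1996 and IQVIA Germany to 1992. No start is given for CPRD GOLD.

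Complete prevalence is a sensitivity analysis with no fixed window. The notes to Table 5 say "For complete prevalence individuals will be considered as a prevalent case if they have ever had a relevant record previously".

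Change over time is part of the purpose. Section 6 warns that "time trends in prevalence may also be present", so that a condition which once met the orphan criterion may no longer do so.

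**The concern.** A 5-year window cannot be filled from a database that is less than five years old. Where the window is cut short, the estimate is a 3- or 4-year prevalence carrying a 5-year label. When the window fills at a later index date, the series can step up with no change in the population.

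Complete prevalence has a related problem. Its look-back is whatever the database happens to hold, so it grows by a year at each index date and can pick up more long-standing cases each time.

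Both effects, if they act as expected, point the same way as the change the study is looking for: prevalence rising towards or past 5 in 10,000. Because data starts differ between sources, the artefact also differs between sources and could be taken for a real difference in trend between countries. SIDIAP is a large contributor (5.8 million active subjects in Table 2) and the only source listed there with hospital linkage.

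**Working it through.** **Inputs.** Index dates are each 1 January from 2010 (sections 8.3 and 8.8). The window is 1,825 days (section 8.6.2). Data starts are from section 8.2, which gives years but no day or month. Survival figures are the protocol's own: follicular lymphoma 15 to 20 years and AML about 1 in 4 alive at 5 years (section 8.6.2); myeloma median 30 to 60 months (Appendix I).

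**The plan's figure.** 5 × 365 = 1,825 days, as stated.

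**Step 1: days of data available.** Days from data start to index date, for the earliest and latest start the stated year allows:

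| Source | Data start | 1 Jan 2010 | 1 Jan 2011 | 1 Jan 2012 |
|---|---|---|---|---|
| SIDIAP | 1 Jan 2006 | 1,461 (364 short) | 1,826 | 2,191 |
| SIDIAP | 31 Dec 2006 | 1,097 (728 short) | 1,462 (363 short) | 1,827 |
| Belgium | 1 Jan 2005 | 1,826 | 2,191 | 2,556 |
| Belgium | 31 Dec 2005 | 1,462 (363 short) | 1,827 | 2,192 |

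The 1,826-day cells have one day of slack, so a start on 2 January would just fill the window and any later start would not. SIDIAP 2010 is short on every reading, and SIDIAP 2011 and Belgium 2010 only on some. Germany (6,575 days from 1 January 1992) and IPCI (5,114 days from 1 January 1996) are full in 2010.

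**Step 2: size for 5-year prevalence.** Assume constant incidence, exponential survival with hazard k, no migration, and no old case re-recorded as new after database start. With L years of look-back, the captured share of 5-year prevalence is (1 − e^(−kL)) / (1 − e^(−5k)).

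- Follicular lymphoma, L = 4, mean survival 15 years: 0.234 / 0.283 = 0.826.
- Follicular lymphoma, L = 4, mean survival 20 years: 0.181 / 0.221 = 0.819.
- Reading 15 to 20 years as a median instead gives 0.818 and 0.814.
- Myeloma: 0.851 to 0.893. AML: 0.893.
- With L = 3 (the latest SIDIAP start), follicular lymphoma falls to 0.62-0.64.

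The artificial step when the window goes from four years to full is 1/0.826 − 1 = 21% to 1/0.819 − 1 = 22% for follicular lymphoma, or roughly 20%.

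**Step 3: size for complete prevalence in SIDIAP.** Under the same assumptions and a start on 1 January 2006, the captured share is 1 − e^(−kL), so the artificial yearly rise is (1 − e^(−k(L+1))) / (1 − e^(−kL)) − 1. The follicular lymphoma range covers both the mean and the median reading.

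| Cancer | 2010 to 2011 (L 4 to 5) | 2015 to 2016 (L 9 to 10) | 2020 to 2021 (L 14 to 15) |
|---|---|---|---|
| Follicular lymphoma | 21-23% | 8-9% | 4-6% |
| Myeloma | 12-18% | 2-5% | 0.5-2% |
| AML | 12% | 2% | 0.5% |

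**Step 4: does anything planned already deal with it?** The history sensitivity analyses require 0 or 1,095 days, both below 1,825. Section 11 mentions arbitrary durations and recovered patients, but not short or lengthening look-back. The planned 2-year partial series does escape the database-start problem: it needs 730 days, and SIDIAP has at least 1,097 on 1 January 2010.

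**The case against.** The case for leaving the plan alone has several sound parts. The 5-year defect touches one SIDIAP index date, or two. Complete prevalence is only a sensitivity analysis. The orphan criterion applies at the time of application, so the latest estimates matter most, and by then the database-level window is full. Results are presented by database, so an early SIDIAP point could be set aside at reporting. The 2-year partial series already offers a fixed-window trend from 2010. All of this stands and limits the consequence. None of it makes the SIDIAP 2010 figure a 5-year prevalence.

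The size, and even the direction, can also be challenged. Cases are found from records. Follicular lymphoma is described as relapsing, and the myeloma, CLL and AML code lists contain history-of-disease codes. A patient diagnosed before 2006 may therefore get a first captured record afterwards and be counted as new, which would push early estimates up. The percentages above are therefore illustrations, not forecasts.

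Three stronger readings are tempting and unsupported:

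- **Belgium is truncated.** The protocol gives only the year 2005. A start on 1 January 2005 leaves 1,826 days, which is enough. Belgian observation time does begin at each person's first consultation, but short person-level history arises beyond Belgium 2010 and is a separate matter that database start dates would not cure.
- **Complete prevalence rises every year simply because look-back lengthens.** The component shrinks yearly, is about 0.5% for AML by 2020-21, and adds to whatever real change exists.
- **Follicular lymphoma would show a near threefold false rise.** Taking L from 4 to 16 gives 0.656/0.234 = 2.80 or 0.551/0.181 = 3.04. That needs an assumed 2022 end date, 16 years of look-back for everyone (SIDIAP's mean follow-up is 10 years), and no re-recording of old cases. It is an upper-end illustration.

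**Conclusion.** The point holds in limited form. On the protocol's own dates, the SIDIAP 5-year estimate for 1 January 2010 is 364 to 728 days short of its window. The 2011 estimate is up to 363 days short unless collection began on 1 or 2 January 2006. Belgium's 2010 estimate is in doubt only because its start day is not stated. These shortfalls are calendar arithmetic and need no model.

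The effect on the estimates does need one. Under steady state and exponential survival, with no old case re-recorded as new, SIDIAP's 2010 figure for follicular lymphoma would capture about 82-83% of 5-year cases at best, followed by a step of roughly 20% when the window fills. Recording of old diagnoses at database start could shrink or reverse this. In SIDIAP complete prevalence, the look-back component is at most about 21-23% for follicular lymphoma in 2010-11 and 4-6% in 2020-21, and about 0.5% for AML by then. The protocol neither handles nor mentions either effect, although it intends to measure prevalence over time.

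**What to change.** In section 8.3, start each database's 5-year partial series at the first 1 January with at least 1,825 days since that database's data start, and state the exact start dates, including CPRD GOLD's. For SIDIAP this means 2011 if collection began on 1 or 2 January 2006, and 2012 otherwise. For Belgium it means 2010 or 2011 by the same rule applied to 2005. Germany and IPCI keep 2010.

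Label complete prevalence as a lower bound that is not to be read as a time trend. Base statements about trend on the fixed-window partial series, including the 2-year series already in Table 5. Add short and lengthening look-back to section 11.

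The cost is one or two annual points in one or two databases, plus a database-specific start date in the code. No new window length is needed, and the planned complete-prevalence output can stay.

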8.4 Follow-up

Study participants will begin contributing person time on the respective date of the latest of the following: 1) study start date (1st January 2010), 2) date at which they have sufficient prior history (365 days, or if there is no requirement for prior history this date will coincide with the date at which their observation period starts), 3) date at which they reach a minimum age (where age strata are being considered). Participants will stop contributing person time at the earliest date of the following: 1) study end date (end of available data in each of the data sources), 2) date at which their observation period ends, 3) the last day in which they have the maximum age (where age strata are being considered). Where there are multiple age strata, study participants will contribute to each strata while they satisfy the conditions of that strata (i.e. when they reach the limit of one age strata they will begin contributing to the next).

An overview of study entry and exit is shown below in **Figure 1** for the overall analysis, with entry of exit for a given age strata shown in **Figure 2**. In this latter example person ID 1 and 3 enter the study on the day they reach the minimum age and exits at the study end date. Person ID 2 enters the study on the study start date and exits at the maximum age. Person ID 4 enters the study on the day they reach the minimum age and leaves when they exit the database (the end of their observation period). Person ID 5 enters the study on the day they have sufficient prior history and exits at the study end date. Lastly, person ID 6 has two observation periods in the database. For the first they enter and contribute time until their exit, for the second they start contributing time again once they have sufficient prior history and exit at the maximum age.

	D2.2.3 – Study Protocol for C1-001	
	Author(s): [name], [name], [name], [name]	Version: 2.0 - Final
	Dissemination level: Public	

[figure not shown]

Figure 1 Included observation time for study participants overall

	D2.2.3 – Study Protocol for C1-001	
	Author(s): [name], [name], [name], [name]	Version: 2.0 - Final
	Dissemination level: Public	

[figure not shown]

Figure 2. Included observation time for study participants for a given age strata

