8.5 Study Population with inclusion and exclusion criteria

All persons in a database will be eligible for inclusion in the study. They will though only enter the study if they have some observation time during the study period. For the primary analysis, study participants will be required to have a year of prior history observed before contributing observation time. This is to ensure a minimum prior observation time to identify any ongoing outcomes (i.e. rare blood cancer) at the time at which a participant enters the study. In sensitivity analyses the requirement for prior history will first be removed, and then increased to three years.

Table 3. Operational Definitions of Inclusion Criteria

Criterion	Details	Order of application*	Assessment window	Care Settings	Code Type	Diagnosis position	Applied to study populations:	Measurement characteristics/ validation	Source for algorithm
Prior database history	Study participants will be	After	1 year	Primary care and combination of	N/A	N/A	All individuals within the	N/A	N/A

	D2.2.3 – Study Protocol for C1-001	
	Author(s): [name], [name], [name], [name]	Version: 2.0 - Final
	Dissemination level: Public	

of 1 year	required to have a year of prior history observed before contributing observation time			primary and secondary care for IQVIA Germany			selected databases		
-----------	--	--	--	--	--	--	--------------------	--	--

* After as first possible study entry date is selected and then it is checked whether patient has one year of database history. In a sensitivity analysis, this rule will be removed. In another sensitivity analysis, required history will be increased to 3 years. N/A: not applicable for this study or data sources being used

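### In the two IQVIA databases a person counts on 1 January only if a later consultation is already recorded, so the last one or two index dates can drift by an artefact whose direction depends on attendance

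*Protocol*

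**What the plan says.** Section 8.2 describes both IQVIA sources in the same way: "Observation time is defined by the first and last consultation dates". The Dutch source differs: "The observation period for a patient is determined by the date of registration at the GP and the date of exit/death". SIDIAP likewise runs from database start or assignment to a centre until transfer-out, death or end of follow-up. Neither of these two depends on attendance.

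Section 8.4 ends a participant's contribution at the earliest of several dates, one being the "date at which their observation period ends". Section 8.5 adds, for the primary analysis, that "study participants will be required to have a year of prior history observed before contributing observation time". Section 8.8 sets the primary estimate: "In this study the primary analysis will use point prevalence, estimated as of the 1st January of each calendar year". Section 8.3 gives the range of dates: "The study period will be between 1st January 2010 and the end of available data in each of the data sources". No margin is left before the end of data.

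Two period-prevalence versions are planned as sensitivity analyses. The first: "Period prevalence will first be estimated with participants required to contribute a minimum of only one day of the period to be included". In the second, "we will estimate period prevalence with participants required to be observed for the full period for them to be included".

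**The concern.** In Belgium and Germany, being in the population on 1 January depends on an event after that date. Someone registered, alive and well who has not yet come back is absent. For an early index date there are years in which to return; for the last one there may be only months. If cases and non-cases attend at different rates, the two groups are lost unevenly, and more so towards the end of the series.

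The recent dates matter because section 6 sets the study against a threshold of 5 in 10,000 at the time of an orphan application, and measuring prevalence over time is an aim. An artefactual rise would look like the increase that section 6 reports from earlier work. IPCI and SIDIAP lack this feature, so comparisons between countries are also affected.

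Nothing in the protocol deals with it. The runs in Table 5 vary outcome duration, prior history and period observability, but none changes how observation ends. Section 11 discusses outcome recording and outcome duration, not the denominator. The checklist in Appendix II marks selection bias as not applicable.

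**Working it through.** The protocol gives no figure on this point, so there is none to reproduce. The calculation turns its rules into an inclusion probability.

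**From the protocol.** Observation ends at the last consultation (8.2); exit is at the end of observation (8.4); index dates are every 1 January (8.8) up to the end of data (8.3); 365 days of prior history are required (8.5); the Belgian data start in 2005 and the German data in 1992 (8.2).

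**Assumed, not in the protocol.** Visit rates per year, c for cases and n for non-cases, with Poisson visits; and the gap d in years from index date to end of data.

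**Step 1: formula.** P(at least one consultation between the index date and end of data) = 1 − exp(−rate × d). For a rare condition, observed/true prevalence ≈ [1 − exp(−c·d)] / [1 − exp(−n·d)]. The prior-history condition is left out here and added in Step 3.

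**Step 2: results.**

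| c, n | d = 0.5 | d = 1 | d = 2 |
|---|---|---|---|
| 10, 1 | 0.993/0.393 = 2.52 | 1.58 | 1.16 |
| 3, 1 | 0.777/0.393 = 1.97 | 1.50 | 1.15 |
| 10, 3 | 0.993/0.777 = 1.28 | 1.05 | 1.00 |
| 3, 2 | 0.777/0.632 = 1.23 | 1.10 | 1.02 |
| 3, 3 | 1.00 | 1.00 | 1.00 |
| 1, 3 | 0.393/0.777 = 0.51 | 0.67 | 0.87 |
| 10, 0.5 | 0.993/0.221 = 4.49 | 2.54 | 1.58 |

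The first four rows are the range used here: cases attend more often and non-cases attend 1-3 times a year. The next two show that the direction is not fixed. The last shows a larger effect when non-cases attend less than once a year.

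**Step 3: whole series.** True prevalence is held at 5.0 per 10,000, with data from 2005 to an assumed mid-2022 and cases at 6-10 visits a year. Inclusion now also needs a first consultation at least one year before the index date. For Poisson visits it is (1 − exp(−rate × past)) × (1 − exp(−rate × future)).

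| Non-case visits per year | 2010 | 2018 | 2020 | 2021 | 2022 |
|---|---|---|---|---|---|
| Poisson, 3 | 5.0 | 5.0 | 5.0 | 5.1 | 6.1-6.4 |
| Poisson, 1 | 5.1 | 5.1 | 5.5 | 6.4 | 12.1-12.6 |
| gamma-Poisson, mean 4, shape 1 | 5.3 | 5.3 | 5.5 | 5.8 | 7.1-7.5 |
| gamma-Poisson, mean 2, shape 0.7 | 6.1 | 6.1 | 6.6 | 7.3 | 10.3-10.8 |

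Most of the rise falls at the last one or two dates. In the gamma rows attendance varies between people, and many attend rarely; the level is then somewhat raised throughout. With cases at 1 and non-cases at 3 visits, the 2022 value falls to 2.5.

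**Step 4: the period-prevalence runs.** With 365 days of history, the one-day version still needs a consultation on or after 1 January. The full-year version needs one on or after 31 December, which is stricter. Neither removes the dependence.

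**The case against.** The strongest objection concerns direction. What counts is attendance at the provider whose record holds the cancer code. Section 8.2 lists the German specialties without naming haematology or oncology, and says that patients seen by several providers are not linked. A patient followed mainly in hospital may attend the contributing practice seldom. This stands. A reader might infer that prevalence must rise, or that it is inflated 2.5 times, but the protocol supports neither. The upward direction is a plausible assumption, and 2.5 needs 10 against 1 visits a year and a 6-month gap. At 3 visits for non-cases the same formula gives 1.28, and 1.05 at 12 months.

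It can also be said that no decision rule is tied to the last IQVIA date and that section 8.9 reports each database separately. Both are true, so the artefact does not enter a pooled figure. It still enters the Belgian and German trends and any comparison of them with other databases.

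Two stronger remedies are tempting. One would declare every IQVIA estimate unfit to set against 5 in 10,000; the working does not support that for the whole series, since most of the distortion sits at the end. The other would drop the full-year runs; they show the effect of observability and are worth keeping with a note.

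Finally, single-visit patients are excluded under the 365-day and 1,095-day requirements, but can count in the one-day runs with no history requirement.

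**Conclusion.** The dependence on a later consultation follows directly from sections 8.2, 8.3, 8.4 and 8.8, and no planned analysis corrects it. Its direction and size are conditional. Under the assumed rates, with cases attending more often than non-cases, inflation is roughly 1.2-2.5 times at 6 months before data end, 1.05-1.6 times at 12 months and about 1.2 times or less at 24 months. It tends to nothing as the two rates approach each other, is larger if non-cases attend less than once a year, and reverses if cases attend less often. The actual end-of-data dates and visit rates are not in the protocol, so no single figure can be given. The last one or two IQVIA index dates should not be read as current prevalence without correction or a flag.

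**What to change.** For IQVIA LPD Belgium and IQVIA DA Germany only:

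- End the main reported series at the last 1 January at least 24 months before the end of data, or show later dates only as flagged provisional estimates. Under the rates above this holds inflation to about 1.2 or less; at 0.5 visits a year for non-cases it would still be about 1.6.
- Add a sensitivity run that extends observation after the last consultation, either by a fixed time or to the practice's end of data.
- State in section 11 that the denominator in these databases is people with repeat attendance, and that the direction of the resulting bias depends on how often cases attend the contributing practice.
- Keep the full-year period-prevalence runs, noting that here they need a consultation on or after 31 December.

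The cost is one or two fewer calendar years in the main series of two databases and a little more analysis work. The other databases need no change on this account.
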